Title: Renal safety of bowel preparation with polyethylene glycol for outpatient colonoscopy: an observational prospective study

Clinical trial registration name and number: NCT02657564

Date: 11/18/2015

Study Protocol

Colonoscopy has been shown to decrease CRC incidence and mortality by the removal of adenomatous polyps. Bowel cleansing is imperative procedure for colonoscopy examination. Oral sodium phosphate and polyethylene glycol (PEG) are the most frequently used bowel purgatives. Oral sodium phosphate preparations are hyperosmotic and promote colonic evacuation by drawing large volumes of water into the colon (1-1.8 L of water per 45 ml of preparation). Oral sodium phosphate preparations are associated with electrolyte imbalance as well as acute phosphate nephropathy, and the latter could be irreversible, requiring dialysis in some cases. The United States FDA warned that over-the-counter oral sodium phosphate products should not be used for colonoscopy bowel preparation which had led to the manufacturer to withdraw from the United States market.

Currently, polyethylene glycol (PEG) solutions have become the most commonly used preparations for colon cleansing and their renal safety has been shown to be better than that of the sodium phosphate [8,11]. PEGs are non-absorbable isosmotic solutions that pass through the bowel without net absorption or secretion. Significant fluid and electrolyte shifts are therefore attenuated. There is no boxed warning regarding PEG use. PEG preparations can be used in patients with renal function impairment, congestive heart failure, or liver cirrhosis. However, several studies have shown that PEG and oral sodium phosphate share comparable renal safety profile. In addition, one recent population-based study reported that the use of PEG was associated with an increased risk of acute kidney injury (AKI).

The primary aim of this clinical trial is to investigate the incidence and reversibility of AKI among adult patients undergoing colonoscopy with 3-L PEG preparation. The secondary study aim is to evaluate the incidence and severity of electrolyte disturbance with 3-L PEG bowel preparation.

METHODS

Patients

This prospective, investigator-initiated clinical trial will be conducted at Evergreen General Hospital since January 2016. Subjects 40 yrs of age or older scheduled for elective colonoscopy, competent to provide written informed consent, and able to communicate effectively with study personnel are eligible for participation in the study.

Patients are considered ineligible for study participation if any of the following were present: severely reduced kidney function (an estimated glomerular filtration rate [GFR] <30 mL/min/1.73 m²); serum electrolyte abnormalities at screening; uncontrolled congestive heart failure (American Heart Association Classification III or IV); unstable angina; untreated dysrhythmia; current use of digitalis preparations or medications known to prolong QT interval; myocardial infarction, percutaneous transluminal coronary angioplasty, or coronary artery bypass graft surgery within the previous 3 months; ascites; current acute exacerbation of chronic inflammatory bowel disease; toxic colitis or toxic megacolon; ileus and/or acute obstruction or perforation; ileostomy, right or transverse colostomy, subtotal colectomy with ileosigmoidostomy and/or ≥50% of colon removed; idiopathic pseudo-obstruction; history of gastric stapling or bypass procedure; difficulties swallowing; treatment with an investigational drug or product; participation in a drug study within 30 days prior to receiving study medication; treatment with another bowel preparation within 21 days prior to colonoscopy; known allergy or hypersensitivity to PEG solution; or any other clinically significant disease or finding that, in the opinion of the investigator, would expose the patient to an increased risk of significant adverse event or would interfere with the assessments of the safety during the course of treatment.

PEG Preparations and Colonoscopy Sedation

A split-dose of the bowel preparation with PEG is provided for morning colonoscopy and a same-day preparation is provided for afternoon colonoscopy. Three sachets of PEG dissolved in 3 L of water are used for colon preparation. After completion of PEG ingestion, additional clear liquids are allowed as desired until 2 hours before the schedule time of the colonoscopy. Moderate conscious sedation with fentanyl and midazolam is provided for all endoscopic procedures.

Participant Flow and Follow-up

Screening visit (up to 28 days before colonoscopy; Visit 1)

The following will be obtained or performed at the screening visit: written informed consent, complete medical history, physical examination, vital sign measurements, information regarding concomitant medications received in the past 7 days, information regarding contrast media exposure in the past 3 months, and blood specimen for serum chemistry analysis. A urine pregnancy test will be performed for women of childbearing potential. Patients receive 3 sachets of PEG and are instructed to consume the PEG preparations according to their colonoscopy schedule by study personnel. Each patient is provided with written dietary and PEG instructions.

Colonoscopy (Visit 2)

Immediately before colonoscopy and before each patient is sedated, study staff perform or obtain patient medical history, complete physical examination, vital sign measurements, information regarding concomitant medications received since the screening visit, and specimens for serum chemistry analysis. Patient will complete a questionnaire concerning their experience with PEG on 5-point Likert scale (1 = severely distressing, 2 = distressing, 3 = bothersome, 4 = mild, and 5 = no symptoms). Compliance is assessed by measuring the volume of PEG solution remaining.

Immediately following the colonoscopy, the investigators assign a score for the overall quality of colon cleansing using Boston bowel preparation scale (BBPS). An excellent bowel preparation is defined as a total BBPS score of 8 or higher, a good preparation as a total score of 7, a fair preparation as a total score of 6, and a poor preparation as a total score of 5 or less.

Follow-up (up to 28 days after colonoscopy; Visit 3)

The following will be obtained or performed at the follow-up visit: physical examination, vital sign measurements, information regarding concomitant medications received after colonoscopy, and blood specimen for serum chemistry analysis.

Data Analysis and Definition

The serum creatinine level on visit 1 is recorded as the baseline renal function. Parameters used for assessing the renal function are change in serum creatinine value (differences between visit 2 and visit 3 from baseline serum creatinine levels) and per cent change in creatinine value (the percentage change of serum creatinine compared to baseline value). AKI is defined as $\geq 50\%$ increase in baseline serum creatinine. The proportion of patients with $\geq 25\%$ increase above their baseline creatinine level will also be identified. In addition, We will compare the change in the estimated GFR (differences between visit 2 and visit 3 from baseline GFR value). The GFR is estimated using the Modification of Diet in Renal Disease Study Group (MDRD) formula. Assessment of changes in serum electrolyte values (including calcium, phosphate, chloride, magnesium, sodium, potassium) between visit 2 and visit 3 from baseline values are also performed. The incidences of electrolyte disturbance will be evaluated.

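### With creatinine measured after PEG only just before colonoscopy and once in the following 28 days, a transient AKI could be missed, and an AKI first found at follow-up cannot be shown to reverse

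*Protocol*

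**What the plan says.** In its opening section the Protocol names, as its main purpose, the "incidence and reversibility of AKI" in adults who take 3 L of PEG before the procedure.

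Its endpoint, in Data Analysis and Definition: "AKI is defined as $\geq 50\%$ increase in baseline serum creatinine", with "The serum creatinine level on visit 1 is recorded as the baseline renal function". The definition has no time window. Changes in creatinine are taken at Visits 2 and 3 against that baseline. The same section also plans the proportion with a rise of at least 25% and the change in estimated GFR.

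The sampling times, in Participant Flow and Follow-up:
- Baseline: "Screening visit (up to 28 days before colonoscopy; Visit 1".
- Visit 2: "Immediately before colonoscopy and before each patient is sedated". Under PEG Preparations and Colonoscopy Sedation, morning patients take a split dose, while "a same-day preparation is provided for afternoon colonoscopy".
- Visit 3: "Follow-up (up to 28 days after colonoscopy; Visit 3". Only a latest day is given.

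Neither document plans a sample between Visits 2 and 3, a repeat after a raised value, or a record of when PEG was started and finished and when blood was drawn. The SAP plans 1152 subjects, to detect an AKI incidence of 0.2% with 90% power.

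**The concern.** Creatinine builds up over hours after filtration falls. In a same-day patient, the Visit 2 sample comes only hours after the first PEG, so an injury may not yet have produced a 50% rise. The next sample may be on day 2 or day 28; both comply. By then a reversible episode may be over.

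Both halves of the primary aim are exposed. Incidence loses any AKI confined to the interval between the two samples, and those are the cases that reverse. Reversibility cannot be judged in a patient whose AKI first appears at Visit 3. With only about two cases expected, one or two unseen cases would change the result, and a low or zero count could be read as renal safety when it partly reflects sampling times.

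**Working it through.** **1. Reproduce the plan's figure.** Inputs from the SAP: incidence 0.2%, power 90%, N = 1152. Reading power as the chance of seeing at least one case:
- Poisson: N = −ln(0.10)/0.002 = 1151.3, rounded up to 1152, an exact match.
- Binomial: N = ln(0.10)/ln(0.998) = 1150.1, rounded up to 1151. At N = 1152, 1 − 0.998^1152 = 0.900.
- Expected cases: 1152 × 0.002 = 2.30.

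**2. Let only a share s of cases be visible at Visit 2 or Visit 3.** The documents do not give s, so it is an assumption shown over a range. It also assumes that 0.2% is a true rate. P(at least one) = 1 − (1 − 0.002s)^1152; N for 90% = −ln(0.10)/(0.002s).

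| s | Observed incidence | Expected cases | P(at least one) | N for 90% |
|---|---|---|---|---|
| 1 | 0.200% | 2.30 | 0.900 | 1152 |
| 0.75 | 0.150% | 1.73 | 0.823 | 1536 |
| 0.5 | 0.100% | 1.15 | 0.684 | 2303 |
| 0.25 | 0.050% | 0.58 | 0.438 | 4606 |

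**3. Can Visit 2 be too early?** Assumed one-compartment balance: dC/dt = (G0·C0 − G1·C)/V, abrupt loss at time zero, V = 30 to 42 L, starting GFR 60 to 90 mL/min (3.6 to 5.4 L/h). Time to a 50% rise:
- 50% loss: t = ln 2 × V/(0.5·G0). Shortest 0.693 × 30/2.7 = 7.7 h; longest 0.693 × 42/1.8 = 16.2 h.
- 40% loss: t = ln 4 × V/(0.6·G0). Shortest 1.386 × 30/3.24 = 12.8 h; longest 1.386 × 42/2.16 = 27.0 h.
- 75% loss: t = ln 1.2 × V/(0.25·G0), about 4.1 to 8.5 h.
- Total loss: t = 0.5 × V/G0, about 2.8 to 5.8 h.

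Moderate injury can therefore be below threshold at Visit 2, while severe injury may already be visible.

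**4. Can Visit 3 be too late?** Assume Visit 3 dates are uniform over 28 days and a share f of cases is already visible at Visit 2. The remaining cases are above threshold from day 1 to day b, so s = f + (1 − f)(b − 1)/28.
- f = 0.25: b = 7 gives s = 0.41 and P = 0.61; b = 14 gives 0.60 and 0.75.
- f = 0.5: b = 7 gives 0.61 and 0.75; b = 14 gives 0.73 and 0.82.
- f = 0.75: b = 7 gives 0.80 and 0.84; b = 14 gives 0.87 and 0.86.

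**5. Can cases be added?** If within-person creatinine CV were 10% (assumption), the chance of a 50% rise by variation alone at one visit is 1 − Φ(ln 1.5/(√2 × 0.10)) = 1 − Φ(2.87) = 0.21%. That is 1152 × 0.0021, or about 2.4 patients per visit, as many as the true cases expected. At a CV of 6% or less it is negligible.

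**The case against.** **Direction.** A reader might infer that the primary incidence is underestimated. The documents do not support that as a net statement. Missing AKI between the samples can only lower the count. However, a single baseline that may be 28 days old, no confirmatory sample, and rises from other causes by Visit 3 can raise it. Step 5 shows that the two could be of similar size. This objection stands.

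**Size.** A reader might also go further and say that power falls to 22%, 44% or 68% for episodes lasting 3, 7 or 14 days (s = 3/28, 7/28, 14/28). Those figures need no detection at all at Visit 2 and uniform Visit 3 dates. The documents establish neither, and split-dose patients start PEG earlier relative to the draw. The SAP takes its planning figures from a previous study whose sampling times are not given. If 0.2% was a rate observed under a similarly sparse schedule, multiplying it by s discounts twice. This also stands, so only a range over s is defensible.

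**Mitigation.** The planned analysis of rises of at least 25% would catch some early injury. In the step 3 model, a 50% loss reaches that level in about 3.2 to 6.7 h and a 40% loss in about 4.4 to 9.1 h. This helps interpretation but does not rescue the primary endpoint.

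**Remedy.** It is tempting to say that an early Visit 3 for everyone removes the trade-off between detection and recovery. It does not: with Visit 3 confined to the first week, AKI that begins later goes unseen. Even a 3-day episode would be caught only 3/7 = 43% of the time if dates were uniform over that week.

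None of this supplies a sample between Visits 2 and 3, or after Visit 3.

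**Conclusion.** The point holds as a limit on what the schedule can show. Transient AKI between the two samples could go uncounted. Reversibility cannot be assessed for an AKI first seen at Visit 3; for one seen at Visit 2, it depends on when Visit 3 happens to fall. How many cases are lost, and whether the net bias is downward, cannot be established, because the documents give neither the time course of AKI after PEG nor the actual Visit 3 days. The step 2 table is a conditional range that rests on s and on 0.2% being a true rate; it is not an estimate of the trial's power. The matter deserves action because so few cases are expected and because the wording of the result decides what a low count is taken to mean.

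**What to change.** 1. Obtain one later repeat creatinine in any patient who meets the AKI definition at Visit 2 or Visit 3, at an interval that the sponsor specifies. Cost: 1152 × 0.002, about 2 extra tests, plus any for chance rises (over two visits, at most about 1152 × 0.0041 = 4.8 at the assumed 10% CV).
2. Record the times of PEG start, PEG finish and every blood draw. Report AKI by visit and by days since PEG, and show the distribution of Visit 3 days. Cost: a few data fields and one table.
3. State the primary result as *AKI present at Visit 2 or Visit 3*, not as the incidence of all AKI after PEG. Cost: none.

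Optionally, the sponsor may set a defined, earlier Visit 3 window. This adds no samples, but scheduling becomes tighter and later-onset AKI may be missed, so the choice should be justified in the protocol.

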Title: Renal safety of bowel preparation with polyethylene glycol for outpatient colonoscopy: an observational prospective study

Clinical trial registration name and number: NCT02657564

Date: 11/18/2015

Statistical Analysis

This study is designed to determine the renal safety of 3-L PEG preparations. The power analysis is performed using SAS 9.2 (SAS Institute, Inc, Cary, NC). The sample size is based on results from previous study comparing the AKI incidence between sodium phosphate and PEG. According to this method, a sample size of 1152 subjects would be required to detect an incidence of AKI of 0.2% with a power of 90%. Statistical analysis is performed by 1-way analysis of variance or *t* test to compare continuous variables. Association between 2 dichotomous variables is analyzed by the Fisher exact test. Results are expressed as mean \pm SD.

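### The primary AKI incidence has no planned confidence interval, although only about two cases are expected if the planning rate is right

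*SAP*

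**What the plan says.** The Protocol's opening section sets the target: "The primary aim of this clinical trial is to investigate the incidence and reversibility of AKI" in adults who all receive the same 3-L PEG preparation. There is no second treatment group.

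The Protocol, under Data Analysis and Definition, defines AKI as a rise of at least 50% in serum creatinine and fixes the reference value: "The serum creatinine level on visit 1 is recorded as the baseline renal function". It also promises the proportion of patients with a rise of at least 25% ("increase above their baseline creatinine level will also be identified") and the changes in creatinine and estimated GFR at visits 2 and 3. It does not say which of those visits decides whether a patient has had AKI.

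The SAP is a single paragraph. On size it says: "The sample size is based on results from previous study comparing the AKI incidence between sodium phosphate and PEG", and concludes that "a sample size of 1152 subjects would be required to detect an incidence of AKI of 0.2% with a power of 90" per cent. For continuous variables it names one-way ANOVA or the t test. For binary data it names one method: "Association between 2 dichotomous variables is analyzed by the Fisher exact test". On presentation it says "Results are expressed as mean" with SD. Neither document mentions a confidence interval.

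**The concern.** The main result will be one proportion from one group. Fisher's test needs a second binary variable and returns evidence of association, not a bound on a rate. ANOVA and the t test compare means. A mean with SD does not describe the uncertainty of a rare proportion. The primary result therefore has no planned measure of uncertainty.

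This matters because the count will be very small if the planning rate is right. With so few cases, what the study can say about safety is carried almost entirely by the upper limit of the interval. A report of 0% or 0.17% without that limit would look more reassuring than the data allow. The power sentence adds to the risk: no null rate, alpha or sidedness goes with it, so a reader could take it to mean that the study will establish a rate near 0.2%.

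**Working it through.** **Inputs.** From the SAP: n = 1152, rate p = 0.002, probability 90%. From the Protocol: one group, binary AKI outcome. Assumed for the calculation: all 1152 are evaluable and the true rate is 0.2%.

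**1. Reproducing 1152.** The probability of at least one case is 1 − (1 − p)^n.

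- At n = 1152: 1 − 0.998^1152 = 0.9004.
- Solving for n, exact binomial: ln(0.10)/ln(0.998) = 1150.1, so 1151.
- Solving for n, Poisson: −ln(0.10)/0.002 = 1151.3, so 1152.

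The stated number follows from the SAP's own two inputs, with no null rate or alpha, if detecting means seeing at least one case. The SAP does not say that this was the method.

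**2. Expected count.** 1152 × 0.002 = 2.3 cases. The chance of none is 0.998^1152 = 0.0996. The chance of two or fewer is 0.0996 + 0.2300 + 0.2653 = 0.595.

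**3. What each result would show.** For x cases, the Clopper-Pearson 95% limits are the 0.025 quantile of Beta(x, n − x + 1) and the 0.975 quantile of Beta(x + 1, n − x). For x = 0 the lower limit is 0 and the upper is 1 − 0.025^(1/1152) = 0.32%.

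| Cases of 1152 | Proportion | Exact 95% interval | Chance of this count at 0.2% |
|---|---|---|---|
| 0 | 0% | 0 to 0.32% | 10.0% |
| 1 | 0.09% | 0.002% to 0.48% | 23.0% |
| 2 | 0.17% | 0.02% to 0.63% | 26.5% |
| 3 | 0.26% | 0.05% to 0.76% | 20.4% |
| 4 | 0.35% | 0.09% to 0.89% | 11.7% |
| 5 | 0.43% | 0.14% to 1.01% | 5.4% |

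These counts cover 97% of the probability at 0.2%. The likeliest result, 2 cases, is compatible with a rate about three times the planning value (0.63/0.2 = 3.1).

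**4. Choice of interval.** The simple normal-approximation interval for 2/1152 has a lower limit of −0.07%, which is impossible. Wilson gives 0.05% to 0.63%, close to the exact upper limit. The method is therefore worth naming in advance.

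**The case against.** The strongest reply is that silence is not a prohibition. The SAP is one paragraph and nothing in it forbids an interval. The mean-and-SD sentence is naturally read as applying to continuous variables. The Protocol already commits to reporting proportions, and anyone given the cases and the denominator can compute the exact interval. This stands in part: no data are lost, and one cannot say that the study would necessarily report an unqualified percentage. But naming the interval and denominator in advance settles the method, who is evaluable and which visit counts before the results are known.

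A second reply is that the sample size is sound. This stands too. A reader might infer from the missing null and alpha that 1152 is miscalculated or cannot be derived, but step 1 reproduces it from the stated inputs. One-sample tests can also be made to land nearby: a null of 0.8% at one-sided 5% gives n = 1153.6, and a null of 0.92% at two-sided 5% gives 1152.05. Those nulls were found by searching for a fit and appear in neither document, so they are not evidence that such a test was used. The SAP also cites a comparative study as its source, and what that study supplied cannot be judged from the documents. The basis therefore stays open, and the sentence is loosely worded rather than shown to be wrong.

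**Conclusion.** The concern holds for the analysis: no listed method yields an interval for the primary AKI proportion. At a true rate of 0.2% with 1152 evaluable, 2.3 cases are expected and the likeliest result, 2/1152, has an exact interval of 0.02% to 0.63%. If the true rate differs from 0.2%, the expected count changes, but the interval for a given count does not.

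The documents do not support two stronger conclusions that a reader might draw. One is that the sample size is wrong. The other is that the study fails some required precision: neither document sets an acceptable upper limit for AKI, so any benchmark such as 1% is only illustrative. The same applies to attrition. No loss rate is given, and the 1152 could mean evaluable patients. As an illustration only, a 10% loss would leave 1037 patients and a detection probability of 1 − 0.998^1037 = 87.5%.

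This is a gap in the specification of the primary result, worth closing before analysis. It is not a flaw in the design.

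**What to change.** 1. Make the primary analysis the proportion with AKI among patients who have a visit 1 creatinine and a post-preparation creatinine, naming the visit or visits that count. Give a Clopper-Pearson 95% interval.
2. Base the safety conclusion on the upper limit of that interval, computed on the number actually evaluable.
3. Report reversibility as x of y AKI cases, since y is likely to be too small for a percentage.
4. State the basis of 1152, and let the answer decide the wording. If it was the chance of seeing a case, replace the power sentence with text such as: *With 1152 evaluable patients and a true AKI incidence of 0.2%, the probability of observing at least one case is 90.0%; about 2.3 cases are expected, and the exact 95% interval for 2/1152 is 0.02% to 0.63%.* If a hypothesis test was used, keep the power statement and add the null rate, alpha and sidedness.

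The cost is a few lines of SAP text and one interval, with no extra patients. The downside is that the stated property will read less favourably than a claim of 90% power.
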